7.1.5.1 Criteria for premature patient withdrawal

Patients may voluntarily withdraw from the study or be dropped from it at the discretion of the investigator at any time. Patients may be withdrawn from the study if any of the following occur:

- Death.
- Lost to follow-up.
- Staying in the study would be harmful.
- Patient/guardian decision.
- Physician decision.
- Non-compliance to protocol requirements.
- Protocol deviation.
- Pregnancy.
- Study terminated by sponsor.
- Study treatment has become available through country-specific programmes outside of this clinical trial (applicable to Brazil, France, Germany, India, Italy, Malaysia, Mexico, Peru and Thailand).

Study treatment has become commercially available and reimbursed (when current treatment becomes commercially available and reimbursed in that indication, the patient will have to be withdrawn from the study and will have completed the study as per protocol).

In addition to the general withdrawal criteria, the following criteria may also require study treatment discontinuation:

If any of the criteria below are met during routine examinations that are part of standard of care, study medication should be discontinued immediately. Re-challenge of study medication is prohibited once discontinuation criteria are met.

Hepatic-related discontinuation criteria

- Jaundice or other signs of clinically significant liver dysfunction
- ALT or AST $> 3 \times$ ULN and Total Bilirubin $\geq 2 \times$ ULN and ALP $< 2 \times$ ULN
- ALT or AST $> 5 \times$ ULN and $\leq 8 \times$ ULN persistent for more than 2 weeks
- ALT or AST $> 8 \times$ ULN

QT related discontinuation criteria

- Confirmed QTcF >500 ms and discontinuation recommended by a cardiologist
- QTcF > 480 msec, if the investigator determines it is no longer safe for the patient to continue in the study, based on ECGs, cardiac examination and recommendation from a cardiologist.
- Clinically significant arrhythmias including:
 1. Any ventricular or supra-ventricular tachyarrhythmia associated with symptoms of hemodynamic compromise.
 2. Sustained ventricular tachycardia (>30 s) irrespective of symptoms.
 3. Recurrent non-sustained VT (≥ 3 beats) during any 24-hour monitoring period.
 4. Clinically significant brady-arrhythmia or third degree AV block.
 5. Need to use a drug with known risk of TdP.

Hyperglycemia related discontinuation criteria

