Grade 4 (> 10.0 x ULN)	Omit dose and discontinue patient from study treatment NOTE: If grade 3 or 4 hyperbilirubinemia is due to the indirect (unconjugated) component only, and hemolysis as the etiology has been ruled out as per institutional guidelines (e.g. review of peripheral blood smear and haptoglobin determination), then ↓ 1 dose level and continue treatment at the discretion of the investigator
AST or ALT	
Grade 1 (> ULN - 2.5 x ULN)	Maintain dose level
Grade 2 (> 2.5 - 5.0 x ULN)	Maintain dose level

Recommended dose modifications for pasireotide LAR	
Worst toxicity CTCAE Grade* (value)	Recommended dose modification any time during a cycle of therapy
(>5.0 and ≤ 8 x ULN)	If ALT or AST return to less than 5 x ULN study drug can be resumed and patient can continue study per protocol. If persistent for more than 14 days, discontinue patient from study treatment. In the event of a re-occurrence, discontinue patient from study treatment.
(> 8 x ULN)	Omit dose and discontinue patient from study treatment
Pancreatic	
Pancreatitis	
Grade 1	Maintain dose level
Grade 2	Maintain dose level
Grade 3	Omit dose and discontinue patient from study treatment
Grade 4	Omit dose and discontinue patient from study treatment
Amylase and/or lipase	
Grade 1 (> ULN - 1.5 x ULN)	Maintain dose level
Grade 2 (> 1.5 - 2.0 x ULN)	Maintain dose level
Grade 3 (> 2.0 - 5.0 x ULN)	For asymptomatic: Omit dose until resolved to ≤ Grade 1, then - If resolved ≤ 7 days, then maintain dose level - If resolved > 7 days, then ↓ 1 dose level For symptomatic: Omit dose and discontinue patient from study treatment Omit dose and discontinue patient from study treatment A CT scan or other imaging study to assess the pancreas, liver and gallbladder must be performed within 1 week of the first occurrence of any ≥ CTCAE grade 3 of amylase and/or lipase.
Grade 4 (> 5.0 x ULN)	
Endocrine/metabolic	
Fasting plasma glucose (FPS) or 2-hour postprandial capillary glucose (PPG)	
FPG <126 mg/dL or PPG < 140 mg/dL	Maintain dose level
Grade 1 (> ULN – 160 mg/dL)	Please refer to Appendix 14.2 'Guideline for study drug-induced hyperglycemia'
Grade 2 (> 160 – 250 mg/dL)	
Grade 3 (> 250 – 500 mg/dL)	
Grade 5 (> 500 mg/dL)	
Cardiac	
Cardiac - prolonged QTc interval	
- QTcF > 480 ms and ≤ 500 ms	If at any time a QTcF > 480 ms and ≤ 500 ms is observed a cardiology consultation must be sought to re-evaluate the abnormal ECG finding.

Recommended dose modifications for pasireotide LAR	

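### For D2101 patients, Table 14-12 lets dosing restart after a combined ALT/AST and bilirubin rise for which section 7.1.5.1 requires a permanent stop, and no text found says which prevails

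*Protocol*

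**What the plan says.** Protocol section 7.1.5.1 covers all patients. One of its hepatic criteria is "ALT or AST $> 3 \times$ ULN and Total Bilirubin $\geq 2 \times$ ULN and ALP $< 2 \times$ ULN". When a listed criterion is met at a routine examination, "study medication should be discontinued immediately", and "Re-challenge of study medication is prohibited once discontinuation criteria are met". The lead-in is softer: "the following criteria may also require study treatment discontinuation".

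Appendix 10 applies to patients from D2101. In section 14.10.2, Table 14-12 has separate bilirubin and ALT/AST blocks:

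- Bilirubin 2-3 x ULN and >3-10 x ULN: omit dosing until grade 1 or lower. Then resume at the same dose if this took 7 days or less, or one level lower if longer.
- Bilirubin >10 x ULN: stop. A note attached to this row covers grade 3 or 4 elevation that is unconjugated only, with hemolysis excluded: "then ↓ 1 dose level and continue treatment at the discretion of the investigator".
- ALT/AST, row "Grade 2 (> 2.5 - 5.0 x ULN"): maintain the dose.
- ALT/AST >5-8 x ULN: may resume once below 5 x ULN; stop if it lasts more than 14 days or re-occurs.
- ALT/AST >8 x ULN: stop.

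The table has no combined row and no ALP condition. Section 14.10.2 bases dose changes on the worst preceding toxicity. Appendix 10 also ends treatment after a delay of more than 21 days, allows one dose reduction only, and stops the drug if the toxicity recurs at the lower dose.

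Table 14-11 sends hepatic findings to Appendix 2. For ALT/AST >3 x ULN with bilirubin at least 2 x ULN, that appendix asks for a work-up and repeat tests, and says discontinuation may be needed if the abnormality is seen again on retesting.

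**The concern.** Appendix 2 itself describes a transaminase rise together with a bilirubin rise as a possible sign of drug-induced liver injury. This is the pattern for which a no-re-challenge rule matters most, and Table 14-12 has no row for it.

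Section 6.2 directs sites to Appendices 2-12 for dose modification. A site treating a D2101 patient would go from there to Appendix 10 and on to Appendix 2. The hepatic text on that route does not point back to 7.1.5.1. Appendix 4, on glucose, does.

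Two things are at stake. A patient could be re-exposed after a signal for which the main text bars re-exposure. And if 7.1.5.1 governs, a site that followed the appendix would be recorded under deviation D01 in SAP section 8.1 (hepatic discontinuation criteria met, patient not withdrawn).

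**Working it through.** There is no sample-size or error-rate figure here to reproduce. The check compares the two rules on the same patients.

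**One patient.** Take ALT 4, bilirubin 2.5 and ALP 1, all x ULN.

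- Section 7.1.5.1: 4 > 3, 2.5 >= 2 and 1 < 2, so the combined criterion is met. Stop, no re-challenge.
- Table 14-12: ALT 4 falls in the >2.5-5 band, so maintain. Bilirubin 2.5 falls in the 2-3 band, so omit, then resume at grade 1 or lower. Taking the worse toxicity selects the bilirubin row, which still ends in re-dosing.

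**All bands, ALP <2 x ULN.** I split ALT/AST at the table's own boundaries, including its 14-day rule, and let the more restrictive row govern. Every cell meets the combined criterion, so 7.1.5.1 says stop in all of them. The entries show what Table 14-12 says without the unconjugated note.

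| ALT/AST (x ULN) | Bilirubin 2-3 | Bilirubin >3-10 | Bilirubin >10 |
|---|---|---|---|
| >3-5 | restart | restart | stop |
| >5-8, resolves within 14 days, no re-occurrence | restart | restart | stop |
| >5-8, lasts more than 14 days | stop | stop | stop |
| >8 | stop | stop | stop |

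- Cells: 4 x 3 = 12.
- Conflicts without the note: 2 x 2 = 4.
- With the note (unconjugated only, hemolysis excluded), the two bilirubin >10 cells in the top two rows also become restart or continuation: 4 + 2 = 6.
- Cells where both texts stop: 12 - 4 = 8 without the note, 12 - 6 = 6 with it.

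These are unweighted combinations of bands. They show where the rules disagree, not how often patients would fall there. The 21-day limit, the single reduction and the recurrence stop narrow re-dosing but do not remove it: bilirubin that settles within 7 days leads back to the same dose.

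**Reach.** SAP section 4.1 lists 15 distinct parent studies in Table 2-1 (16 rows, X2404 twice) and 2 in Table 2-2, so 17 in all. D2101 is not among them. D2401 is listed as pituitary adenomas and is not counted as D2101, which is a neuroendocrine tumor study.

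**The case against.** The strongest reply is that 7.1.5.1 plainly governs and the table is only silent. Sections 2.1, 4.1 and 6.1.7 run treatment until a discontinuation criterion is met. Section 6.2 treats the appendices as guidelines, Table 14-12 is headed as recommended, and SAP D01 has no exception for Appendix 10. The >5-8 x ULN row resumes treatment under the protocol, which could be taken to bring in 7.1.5.1. The table's ALT/AST-only stops agree with 7.1.5.1. A site can satisfy both texts by applying the stricter.

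Much of this stands, and 7.1.5.1 is probably meant to prevail. But that has to be inferred. The 7.1.5.1 lead-in is permissive, Table 14-12 is captioned as criteria for re-initiation, and nothing in the available text tells a site to take the stricter rule. The reference to the protocol in the >5-8 row does not help with the >3-5 row or the bilirubin rows.

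A reader might also infer that the table conflicts with the criterion "Jaundice or other signs of clinically significant liver dysfunction", and that the unconjugated note is therefore wrong. The documents do not support going that far. The table never mentions jaundice, and no bilirubin level for jaundice is given. The bullet can be read as jaundice that reflects liver dysfunction, which isolated unconjugated elevation need not be. Whether the note should yield there is a medical decision.

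Nor is the softer wording confined to Table 14-12. The six other AE dose tables (14-1, 14-5, 14-8, 14-9, 14-10, 14-13) exclude LFT increase, so only Table 14-12 has its own hepatic restart rows. Appendix 2, however, reaches all patients, and its text is also weaker than 7.1.5.1 for the combined pattern.

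**Conclusion.** Wrong as written, and minor. For a D2101 patient who meets the combined ALT/AST, bilirubin and ALP criterion, 7.1.5.1 bars further drug. Table 14-12 allows restart when bilirubin of 2-10 x ULN has resolved to grade 1 or lower and ALT/AST was >3-5 x ULN, or >5-8 x ULN resolving within 14 days without re-occurrence.

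Few or no patients may be affected. The SAP is based on Amendment 5 and derives indication from its listed parent studies, so the absence of D2101 suggests, but does not prove, that none enrolled. Appendix 10 is nonetheless current text. It would be wrong to infer that anyone was re-challenged, or that an analysis is affected: no planned summary of AEs or clinical benefit changes.

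The conclusion assumes that the unavailable Figure 14-1, to which Appendix 2 refers, does not settle precedence. It also assumes that sites apply the table rows as printed.

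**What to change.** Add one statement to section 6.2 and repeat it at Table 14-12:

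> Meeting a 7.1.5.1 discontinuation criterion, including the combined ALT/AST-bilirubin criterion, ends study treatment and bars re-challenge, whatever Appendices 2-12 would otherwise allow; stricter appendix stops still apply.

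Naming Appendices 2-12 brings the softer Appendix 2 wording under the same rule. The last clause is needed because Table 14-12 is stricter elsewhere. It requires a stop once a cardiologist confirms mean QTcF above 500 ms, while 7.1.5.1 also needs the cardiologist to recommend discontinuation.

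The sponsor's medical team should separately decide, and state, whether jaundice from isolated unconjugated hyperbilirubinemia counts as the 7.1.5.1 jaundice criterion. Figure 14-1 should be checked against the new statement.

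The cost is a short text change in two places, with SAP D01 left as it is. The downside is that an occasional patient whose combined abnormality resolves loses access to the drug.

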14.10.3 Guidance for diarrhea management

General recommendations:

- Stop all lactose-containing products, alcohol
- Stop laxatives, bulk fiber (Metamucil, Procter & Gamble), and stool softeners (docusate sodium; Colace, Roberts)
- Drink 8 to 10 large glasses of clear liquids per day (water, Pedialyte (Ross), Gatorade (Quaker), broth)
- Eat frequent small meals (bananas, rice, applesauce, Ensure, toast)
- Stop high-osmolar food supplements such as Ensure Plus and Jevity Plus (with fiber)

It is recommended that patients be provided loperamide tablets. It is mandatory that patients are instructed on the use of loperamide at cycle 1 in order to manage signs or symptoms of diarrhea at home. Patients should be instructed to start oral loperamide (initial administration of 4mg, then 2mg every 4 hours (maximum of 16 mg/day) at the first sign of loose stool or symptoms of abdominal pain. These instructions should be provided at each cycle and the site should ensure that the patient understood the instruction. At the beginning of each cycle, each patient should be specifically questioned regarding any experience of diarrhea or diarrhea related symptoms. If symptoms were experienced, then the site should question the patient regarding the actions taken for these symptoms.

Treatment of diarrhea grade 1 or 2

Diarrhea grade 1 or 2 will be treated with standard loperamide (initial at first administration 4 mg, then 2 mg every 4 hours (maximum of 16 mg/day) or after each unformed stool).

12-24 hours later:**Diarrhea resolved**

- Continue instructions for dietary modification
- Gradually add solid foods to diet
- Discontinue loperamide after 12-hours diarrhea-free interval

Diarrhea unresolved

Persisting diarrhea grade 1 or 2 will be treated with addition of opium tincture or dihydrocodeine tartrate tablets/injections with monitoring of patients condition to rule out dehydration, sepsis, ileus) medical check and selected workup if patient does not need hospitalization (see section Diarrhea workup and additional test in the particular trial protocol). Observe patient for response to antidiarrheal treatment.

Persisting diarrhea grade 3 or 4 may be treated with hospitalization, high dose loperamide (initial 4 mg, then 2 mg every 2 hours) and addition of opium tincture or dihydrocodeine tartrate tablets/injections, start of *i.v.* fluids and antibiotics as needed with monitoring of patients condition (to rule out dehydration, sepsis, ileus) medical check and workup (perform appropriate additional testing). Observe patient for response.

After 12-24 hours:**Diarrhea resolved**

- Continue instructions for dietary modification
- Gradually add solid foods to diet
- Discontinue loperamide and/or other treatment after 12-hours diarrhea-free interval

Diarrhea unresolved

- If diarrhea still persisting (NCI CTC grades 1 and 2), after 2x 24 hours with high dose loperamide and opiates then admit to hospital and employ measures as for grade 3 and 4 until diarrhea resolved
- If diarrhea still persisting and progressed to NCI grades 3 and 4, employ measures described below.

Treatment of diarrhea grade 3 or 4

Severe diarrhea grade 3 or 4 may be treated with hospitalization, high dose loperamide (initial 4 mg, then 2 mg every 2 hours and addition of opium tincture or dihydrocodeine tartrate tablets/injections, start of *i.v.* fluids and antibiotics as needed with monitoring of patients condition (to rule out dehydration, sepsis, ileus) medical check and workup (see section Diarrhea workup and additional test in the particular trial protocol). Observe patient for response.

After 12-24 hours:

- If diarrhea persisting administer s.c. Sandostatin/octreotide (100-500 µg tid)

- Continue IV fluids and antibiotics as needed
- If diarrhea grade 3 or 4 still persists patients should receive opium tincture or dihydrocodeine tartrate injections s.c. or i.m.
- If diarrhea grade 3 or 4 is still persisting s.c. Sandostatin/octreotide (500-1000 µg tid) should be administered.
- To control and/or resolve diarrhea, next cycle of treatment should be delayed by 1 or 2 weeks. Treatment should be continued only when diarrhea resolved.

Diarrhea workup

Perform appropriate tests ([Fine and Schiller 1999](#)).

Spot stool analysis

- Collect stool separating it from urine (special containers, analysis immediately, exceptionally freeze samples)
- Blood
- Fecal leukocytes (Wright's staining and microscopy) or
- Clostridium difficile toxin
- Fecal cultures including *Salmonella* spp., *Campylobacter* spp., *Giardia*, *Entamoeba*, *Cryptosporidium* (which can lead to opportunistic infections in immununosuppressed patients), plus *Shigella* and pathogenic *E. coli* - enterotoxigenic, enterohemorrhagic etc., possibly *Aeromonas*, *Pleisiomonas* (if suspected exposure to contaminated water)

Endoscopic examinations

Endoscopic examinations may be considered **only if absolutely necessary**. The bowel is likely to be fragile with evidence of colitis and thus great care and caution must be exercised in undertaking these invasive procedures.

- Gastroscopy to obtain jejunal fluid - re. bacterial overgrowth for cultures and biopsy of proximal jejunum to assess extent of inflammatory jejunitis
- Sigmoidoscopy - reassessment of colitis

14.11 Appendix 11: Dose modification information for patients with Cushing's receiving pasireotide s.c or acromegaly receiving pasireotide LAR (from protocols SOM230B2219 and SOM230B2305)

Cushing's disease: Pasireotide (SOM230) s.c. injection: 300, 600 or 900 μ g b.i.d.; Acromegaly: Pasireotide (SOM230) i.m. LAR: 20, 40 or 60 mg every 28 days

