10.4.2 Statistical hypothesis, model, and method of analysis

No hypothesis will be tested.

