14.10.1 Dose modification and dose delay

The patient should be followed as described in [Table 14-12](#) until the toxicity in question has resolved to CTCAE grade 1 or to the patients' baseline value, or until the toxicity is deemed irreversible.

Patients who cannot be treated with pasireotide LAR within 21 days of the intended dosing day due to drug-related toxicity should have weekly follow-ups that include a physical examination, vital signs including weight, performance status, ECGs, and assessment of adverse events and concomitant medication. Following toxicity, ECG, hematology, renal and liver function tests should be performed as appropriate.

If a patient requires a dose delay of > 21 days from the intended day of the next scheduled dose of pasireotide LAR, then the patient must be discontinued from the study. Patients who discontinue from the study for a study drug-related adverse event or an abnormal laboratory value, must be followed as described in [Table 14-11](#).

For each patient, only one dose reduction will be allowed after which the patient should be discontinued from the study. For each patient, once a dose level reduction has occurred, the dose level may not be re-escalated during subsequent treatment cycles with pasireotide LAR. Dose reduction for pasireotide LAR means treatment at a lower pasireotide LAR dose level. Dose modification for patients treated at the starting dose of 80 mg will be 60 mg.

All interruptions or changes to study drug administration must be recorded on the Dosage and Administration Record eCRF.

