14.10.2 Treatment interruption and treatment discontinuation

All dose modifications should be based on the worst preceding toxicity.

Each patient is only allowed one dose reduction. In addition, a patient must discontinue treatment with pasireotide LAR if, after treatment is resumed at a lower dose, the toxicity recurs with the same or worse severity

Table 14-12 Criteria for interruption and re-initiation of pasireotide LAR

Recommended dose modifications for pasireotide LAR	
Worst toxicity CTCAE Grade* (value)	Recommended dose modification any time during a cycle of therapy
No toxicity	Maintain dose level
Hematologic	
Neutropenia (ANC)	
Grade 1 (ANC < LLN - 1500/mm ³)	Maintain dose level
Grade 2 (ANC < 1500 - 1000/mm ³)	Maintain dose level
Grade 3 (ANC < 1000 - 500/mm ³)	Omit dose until resolved to ≤ Grade 2, then - If resolved ≤ 7 days, then maintain dose level - If resolved > 7 days, then ↓ 1 dose level

Recommended dose modifications for pasireotide LAR	
Worst toxicity CTCAE Grade* (value)	Recommended dose modification any time during a cycle of therapy
Grade 4 (ANC < 500/mm ³)	Omit dose until resolved to ≤ Grade 2, then - If resolved ≤ 7 days, then maintain dose level - If resolved > 7 days, then ↓ 1 dose level
Thrombocytopenia	
Grade 1 (PLT < LLN - 75,000/mm ³)	Maintain dose level
Grade 2 (PLT < 75,000 - 50,000/mm ³)	Maintain dose level
Grade 3 (PLT < 50,000 - 25,000/mm ³)	Omit dose until resolved to ≤ Grade 1, then - If resolved ≤ 7 days, then maintain dose level - If resolved > 7 days, then ↓ 1 dose level
Grade 4 (PLT < 25,000/mm ³)	Omit dose until resolved to ≤ Grade 1, then ↓ 1 dose level
Febrile neutropenia (ANC < 1.0 x 10 ⁹ /L, fever ≥ 38.5°C)	Omit dose until resolved, then ↓ 1 dose level
Renal	
Serum creatinine	
< 2 x ULN	Maintain dose level
2-3 x ULN	Omit dose until resolved to ≤ Grade 1, then - If resolved ≤ 7 days, then maintain dose level - If resolved > 7 days, then ↓ 1 dose level
Grade 3 (> 3.0 - 6.0 x ULN)	Omit dose and discontinue patient from study treatment
Grade 4 (> 6.0 x ULN)	Omit dose and discontinue patient from study treatment
Hepatic	
Bilirubin	
< 2 x ULN	Maintain dose level
2-3 x ULN	Omit dose until resolved to ≤ Grade 1, then - If resolved ≤ 7 days, then maintain dose level - If resolved > 7 days, then ↓ 1 dose level
Grade 3 (> 3.0 - 10.0 x ULN)	Omit dose until resolved to ≤ Grade 1, then - If resolved ≤ 7 days, then maintain dose level - If resolved > 7 days, then ↓ 1 dose level

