Worst toxicity CTCAE Grade* (value)	Recommended dose modification any time during a cycle of therapy
- QTcF > 500 msec	
 1. Triplicate ECGs (2-3 minutes apart) need to be taken approximately 1 hour after the initial ECG. 2. If the mean QTcF is > 500 ms, the patient must postpone study treatment until a cardiologist has re-evaluated the ECG. 3. The re-evaluation of ECG needs to be done as soon as practical but within 7 days of the initial abnormal ECG. 4. If the cardiologist confirms a mean QTcF > 500 ms, the patient must be discontinued.
Cardiac general Grade 1 or 2 Grade 3 Grade 4	
Maintain dose level
 
Omit dose until resolved to ≤ Grade 1, then ↓ 1 dose level
 
Omit dose and discontinue patient from study treatment

Other adverse events	
Grade 1 or 2 Grade 3 Grade 4	
Maintain dose level
 
Omit dose until resolved to ≤ Grade 1, then ↓ 1 dose level
 
Omit dose and discontinue patient from study treatment

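### Appendix 10 gives two incompatible instructions for grade 4 diarrhoea: Table 14-12 ends study treatment, while Section 14.10.3 postpones the next cycle and then continues

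*Protocol*

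**What the plan says.** Protocol Section 6.2 sends sites to Appendices 2 to 12 for dose modification. Appendix 10 (Section 14.10) is the one for neuroendocrine tumour patients coming from SOM230D2101 on pasireotide LAR.

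Table 14-12, in Section 14.10.2, grades toxicities and gives an action for each under the column heading "Recommended dose modification any time during a cycle of therapy". It has haematologic, renal, hepatic, pancreatic, endocrine/metabolic and cardiac rows, and a closing row, "Other adverse events". Neither diarrhoea nor any gastrointestinal event has a row. In the closing row, the grade 3 action is "Omit dose until resolved to ≤ Grade 1, then ↓ 1 dose level" and the grade 4 action is "Omit dose and discontinue patient from study treatment".

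Section 14.10.3 is diarrhoea guidance. Its block for the two highest grades opens with "Severe diarrhea grade 3 or 4 may be treated with hospitalization, high dose loperamide" and goes through supportive care. Its last instruction concerns study treatment: "next cycle of treatment should be delayed by 1 or 2 weeks. Treatment should be continued only when diarrhea resolved". The block does not separate grade 3 from grade 4, states no dose level for resumption and does not mention discontinuation.

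Sections 14.10.1 and 14.10.2 add general rules: decisions follow the worst toxicity that preceded them, each patient may be reduced once, a reduced dose may not be raised again, and recurrence of the toxicity at the same or worse severity on the lower dose ends treatment. None of these rules makes an exception for diarrhoea.

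**The concern.** An investigator treating a D2101 patient with grade 4 diarrhoea finds two answers within one appendix. One ends study treatment. The other holds it for a week or two and continues after recovery. This is a stopping rule for a foreseeable event: protocol Section 2.6 names diarrhoea as a characteristic symptom of many neuroendocrine tumours, and Section 1.2.1.2.2 puts mild diarrhoea among the most commonly reported events in healthy volunteers given the s.c. formulation.

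The choice could also reach the data. SAP Section 7.4.1 tabulates separately the adverse events that led to discontinuation and those that required dose adjustment or interruption. SAP Section 6.1 tabulates patients who met withdrawal criteria but were not withdrawn. A site that follows Section 14.10.3 at grade 4 could be recorded as deviating from Table 14-12, and the same event could fall in different tables at different sites.

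**Working it through.** No arithmetic from the plan is at issue. The protocol has no sample size calculation, and Section 10.4.2 says "No hypothesis will be tested". The check is a comparison of texts.

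| | Table 14-12, closing row | Section 14.10.3, grade 3 or 4 block | Can both be followed? |
|---|---|---|---|
| Grade 4 | Omit and discontinue | Postpone the cycle, continue after resolution | No |
| Grade 3: action | Omit, then resume one level lower | Postpone the cycle, continue after resolution; no dose level given | Yes |
| Grade 3: recovery needed | Grade 1 or lower | Resolved | Yes, by waiting for the stricter condition |

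**Step 1: which row applies.** With no diarrhoea or gastrointestinal row, diarrhoea can only come under the closing row.

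**Step 2: grade 4.** Permanent discontinuation leaves no next cycle to postpone. Later improvement does not remove the conflict, because Section 14.10.2 ties dose modifications to the worst preceding toxicity.

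**Step 3: grade 3.** Both texts hold the dose and both allow resumption. Section 14.10.3 is silent on dose, so the table's reduction can be applied at that point. A site reading Section 14.10.3 alone would not know that a reduction is expected. That matters because only one reduction is allowed and it cannot be reversed.

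**Step 4: is there a conflict with the delay limit?** Section 14.10.1 sets its limit with "If a patient requires a dose delay of > 21 days from the intended day of the next scheduled dose", and discontinuation follows. One to two weeks is 1 × 7 = 7 to 2 × 7 = 14 days, which is below 21. There is no conflict here.

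**Step 5: is there a rule of precedence?** None was found in Appendix 10. Where Table 14-12 defers to other guidance it says so: its glucose rows point to a separate guideline. It has no such pointer for diarrhoea. Appendix 8, whose diarrhoea text is nearly the same, does direct the reader from its dose table to its diarrhoea section. Appendix 10 does not.

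**Step 6: who is affected.** SAP Section 4.1 derives indication from the parent study in Tables 2-1 and 2-2. Neither lists D2101, so the documents give no count of patients under Appendix 10.

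**The case against.** The strongest reply is that the structure of the appendix already gives an answer. Table 14-12 sits in the section on interruption and discontinuation, whereas Section 14.10.3 is titled as guidance and is almost all supportive care. Its last sentence can be read as restricting resumption and not as ordering it. If grade 4 patients stop, the postponement still has a use for grade 3, and for persisting grade 1 or 2 diarrhoea that is escalated to the same measures. This is a reasonable reading, but the reader has to supply it. The block is expressly for grades 3 and 4, and nothing takes grade 4 out of it.

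The table is also headed as recommended modifications, and Section 6.2 leaves dose changes to the investigator's judgement. That softens the force of both texts without reconciling them.

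Three stronger readings are tempting and are not supported:

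- **That grade 3 is also a contradiction, with continuation at full dose under Section 14.10.3.** The section never says full dose. Silence is not an instruction, and both texts can be followed together.
- **That Table 14-12 stops every grade 4 event and reduces after every grade 3 event.** Grade 4 thrombocytopenia is omitted and then reduced, and grade 4 neutropenia may resume at the same level. Grade 3 creatinine and grade 3 pancreatitis are discontinued. The pattern of reducing at grade 3 and stopping at grade 4 belongs to the closing row and the general cardiac row.
- **That one event could be stopped, reduced or continued.** At grade 4 the choice is to stop or to continue. At grade 3 it is a stated reduction or an unstated dose.

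**Conclusion.** The point holds for grade 4 diarrhoea: the two instructions are incompatible and Appendix 10 does not say which governs. For grade 3 there is an ambiguity about dose level and recovery grade.

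The conclusion rests on diarrhoea falling under the closing row of Table 14-12, which follows from the absence of any other row for it.

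The practical size is unknown. A reader might infer a sizeable effect from the diarrhoea rates of 35% and 43% in Section 1.2.1.2.2. Those are any-grade rates from SOM230G2304, in Cushing's disease at 10 mg and 30 mg. Appendix 10 concerns neuroendocrine tumours and names 80 mg as a starting dose. The figures give no grade 4 rate and do not carry over. Since the SAP's parent-study tables do not list D2101, an effect on the SAP's discontinuation and dose-adjustment tables is possible but not shown, and the number affected may be zero. If no D2101 patients are enrolled, the priority falls. Appendix 10 nevertheless remains in the current protocol, and Section 6.2 points sites to it.

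**What to change.** Reconcile Table 14-12 and Section 14.10.3 for grade 4 diarrhoea against the SOM230D2101 parent protocol, which was not available here. State in both places which passage governs discontinuation. For grade 3, state in both places the dose level and the recovery grade at resumption, and whether the episode uses the single permitted reduction. A cross-reference in each direction would prevent the two texts from diverging again. Which rule is right is for the sponsor to decide from the parent protocol.

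The sponsor should also confirm whether any D2101 patients are in the study, since that sets the urgency.

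The cost is a wording change in one appendix at the next amendment, with no new data or patients.
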